| To assess the effect of solanezumab vs. placebo on biomarkers in prodromal AD over 24 months | Changes from baseline to 24 months in florbetapir PET or CSF A β / tau, vMRI, plasma A β , plasma solanezumab, sample storage for biomarkers (where permitted); includes CSF collected via optional addendum |
| To assess the hypothesis that solanezumab will slow the accumulation of tau pathology over 12 and 24 months compared to placebo | Changes from baseline in neocortical tau deposits (collected in a subset of patients using ¹⁸ F-AV-1451 PET as part of an addendum) over 12 and 24 months |
| To assess the hypothesis that change from baseline in accumulation of tau pathology over 12 and 24 months is associated with changes from baseline in cognition | Changes from baseline in neocortical tau deposits (collected in a subset of patients using ¹⁸ F-AV-1451 PET as part of an addendum) and ADAS-Cog ₁₄ , over 12 and 24 months |
| To assess the hypothesis that change from baseline in accumulation of tau pathology over 24 months is associated with changes from baseline in function | Changes from baseline in neocortical tau deposits (collected in a subset of patients using ¹⁸ F-AV-1451 PET as part of an addendum) and ADCS-MCI-ADL over 24 months |
| To assess the effect of pharmacogenomic factors on clinical and functional progression with solanezumab vs. placebo in prodromal AD over 24 months | Changes from baseline in pharmacogenomics markers (where permitted) and clinical and functional scales |

| Objectives | Endpoints |
|---|--|
| 
Exploratory To generate additional data for validation of the Preclinical Alzheimer's Cognitive Composite score (PACC), a composite endpoint being used in another Lilly study To compare MMSE and MoCA scales To assess time to significant progression
 | 
Changes from baseline in components of the MMSE, RBANS, and FCSRT over 24 months Changes from baseline in MMSE and MoCA over 24 months Time to progression to CDR-SB score of 1.0, and significant change on other cognitive, and functional measures
 |

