6.1. Inclusion Criteria

Patients are eligible to be included in the study only if they meet all of the following criteria at screening:

Patient Characteristics and Diagnostic Criteria

- [1] Is aged 55-85 years
- [2] Has a diagnosis by the study investigator of a clinical syndrome of cognitive impairment consistent with prodromal AD per IWG diagnostic criteria or MCI due to AD per NIA-AA diagnostic criteria, confirmed by all of the following:
 - a. Subjective cognitive complaint or informant report of cognitive impairment for at least 6 months prior to Visit 1
 - b. No significant impairment of iADLs by patient and informant report and in the judgment of the investigator (that is, patients are maintaining their independence of functioning in daily life with minimal aids or assistance)
 - c. Not demented, based on IWG or NIA-AA guideline criteria
- [3] Scores 17-28 on Montreal Cognitive Assessment (MoCA) at Visit 1
- [4] Scores <27 on free recall cutoff score from the Free and Cued Selective Reminding Test (FCSRT) (Picture version) at Visit 1
- [5] Scores ≤ 4 on Modified Hachinski Ischemia Scale
- [6] Scores >0 on the Functional Activities Questionnaire (FAQ)
- [7] Has a reliable study partner who is in frequent contact with the patient (defined as at least 10 hours per week), will accompany the patient to the study visits, and will be available by telephone at designated times

Note: Study partners must be able to communicate with site personnel and be willing to comply with protocol requirements, and in the investigator's opinion must have adequate literacy to complete the protocol-specified questionnaires. Study partners must come in person to all visits with assessments that require their input.

- [8] Has a florbetapir PET scan or CSF result at screening consistent with the presence of amyloid pathology (see also Exclusion Criterion [34]). (Note: Previously acquired amyloid PET scans unrelated to Study LZBE may be permitted for use in meeting this criterion. Refer to specific guidance in the manual of operations.)

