Clinical Dementia Rating Scale (CDR-SB; Berg et al. 1992). The CDR is a semi-structured interview performed with the patient and informant that provides an index of global functioning. The informant is queried about the patient’s memory, orientation, judgment and problem solving, community affairs, home and hobbies, and personal care. The patient’s memory, orientation, judgment, and problem-solving ability are assessed. By assigning a severity score for each of the 6 domains, a total score known as sum of boxes is obtained—hence the abbreviation, CDR-SB.

Resource Utilization in Dementia—Lite questionnaire (RUD-Lite; Wimo et al. 1998). The RUD-Lite is an abbreviated version of the Resource Utilization in Dementia (RUD) scale designed to assess the healthcare resource utilization of patients and their caregivers (or in this case, study partners) and to determine the level of formal and informal care attributable to AD. The data are collected through a structured interview. Information on both study partners (caregiving time and work status) and patients (accommodation and healthcare resource utilization) is gathered from the baseline and final assessment interviews. Study partners will be asked to provide data on time spent assisting patients’ basic ADLs such as using the toilet, eating, dressing, grooming, walking, and bathing; assisting patients’ instrumental ADLs such as shopping, cooking, housekeeping, laundry, transportation, taking medication, and managing finances; and providing supervision. The resource utilization quantified by the RUD-Lite can be used for calculating cost offsets and in cost-effectiveness models.

Note that as of 2016, only the full RUD is supported by its copyright owners, such that users who wish to administer a shorter version must pull out questions from the RUD. Study LZBE is administering the short version of the RUD once formally known as the RUD-Lite and will continue to use the name “RUD-Lite” for consistency with other solanezumab protocols that have administered this scale.

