To assess the effect of pharmacogenomic factors on clinical and functional progression with solanezumab vs placebo in prodromal AD over 24 months	Changes from baseline in pharmacogenomics markers (where permitted) and clinical and functional scales

Objectives and Endpoints

Objectives and Endpoints		
Objectives	Endpoints	
Exploratory		
To generate additional data for validation of the	Changes from baseline in components of the MMSE,	
PACC score, a composite endpoint being used in	RBANS, and FCSRT over 24 months	
another Lilly study		
To compare MMSE and MoCA scales	Changes from baseline in MMSE and MoCA over	
	24 months	
To assess time to significant progression	Time to progression to CDR-SB score of 1.0, and significant	
	change on other cognitive and functional measures	

Abbreviations: $A\beta$ = amyloid- β peptide; AD = Alzheimer's disease; ADAS- COG_{14} = 14-item Alzheimer's Disease Assessment Scale-Cognitive subscale; ADCS-MCI-ADL = Alzheimer's Disease Cooperative Study-Mild Cognitive Impairment-Activities of Daily Living Inventory; CDR-SB = Clinical Dementia Rating-Sum of Boxes; CSF = cerebrospinal fluid; EQ-D = EuroQol 5-Dimensional Health-Related Quality of Life Scale; E Functional Activities Questionnaire; E Free and Cued Selective Reminding Test; E MMSE = Mini-Mental State Examination; E MoCA = Montreal Cognitive Assessment; E NPI = Neuropsychiatric Inventory; E Preclinical Alzheimer's Cognitive Composite; E PeT = positron emission tomography; E Q4W = every 4 weeks; E QoL-E Quality of Life in Alzheimer's Disease (scale); E RBANS = Repeatable Battery for the Assessment of Neuropsychological Status; E RUD-Lite = Resource Utilization in Dementia-Lite; E vMRI = volumetric magnetic resonance imaging.

5. Study Design

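### Does the exploratory CDR-SB time-to-progression endpoint need an at-risk rule, since patients may already score 1.0 at randomization?

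*Protocol*

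**What the plan says.** In Protocol Section 4, Table LZBE.1, the exploratory objective is "To assess time to significant progression" and its endpoint is "Time to progression to CDR-SB score of 1.0, and significant change on other cognitive, and functional measures". SAP Table LZBE.4.1 keeps the threshold: "Time to progression to CDR-SB score of 1.0, and significant", followed by the same reference to change on other measures.

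Protocol 9.1.2 describes how the score is built: "By assigning a severity score for each of the 6 domains, a total score known as sum of boxes is obtained". It gives neither the steps of the box scores nor the range of the total.

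Protocol 6.1 limits severity partly by clinical criteria, "No significant impairment of iADLs by patient and informant report" and "Not demented, based on IWG or NIA-AA guideline criteria", and partly by scores. An example of the latter is "Scores 17-28 on Montreal Cognitive Assessment (MoCA) at Visit 1"; the others are FCSRT free recall, the Hachinski scale and the FAQ. None of the inclusion or exclusion criteria uses the CDR.

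The Schedule of Activities places CDR-SB at Visit 2, Visit 15 (Week 52), Visit 28 (Week 104) and early discontinuation. Protocol 10.4.2.1 describes repeated-measures, slopes and categorical analyses and no time-to-event method. It leaves the definitions of decline for the categorical analyses to the SAP.

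SAP 6.1 reports that the sponsor discontinued the study on 10 January 2017 with 26 patients randomized. In general it plans no analysis for any primary, secondary or exploratory efficacy objective.

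**The concern.** The row asks about progression, and its other measures are judged by change. CDR-SB alone is judged by a fixed level. The study enrols people who are already impaired: the FCSRT and FAQ criteria both require some deficit. It is therefore plausible that some patients reach 1.0 at baseline, and nothing in the entry criteria rules it out.

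For such patients the endpoint can be handled in two ways:

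- **Kept.** The event is any postbaseline score of 1.0 or more. An unchanged patient then counts as progressed in either arm, and the contrast between arms is diluted.
- **Dropped.** Progression means moving from below 1.0. The contrast is not diluted, but the analysed set is a subset of those randomized and is not described anywhere.

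The two can give different answers, and neither document chooses between them. With the planned 2450 patients and a full efficacy analysis, the reported result could have depended on a decision made after the data were seen.

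**Working it through.** The documents give no event rate, sample size or power for this endpoint, so there is no figure of the plan's to reproduce.

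**Can a patient be at or above 1.0 at Visit 2?**

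- Criteria with a score limit: MoCA, FCSRT, Hachinski and FAQ, four in all. Criteria using CDR or CDR-SB: none.
- The requirements on dementia and on instrumental activities limit severity by judgment and are not tied to a CDR-SB value.
- So the documents allow it. They give no baseline CDR-SB distribution, so the share p cannot be derived.

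**Size of the dilution if such patients are kept.** Let p be the share at or above 1.0 at Visit 2, all assumed to stay there. Let e_c and e_t be the event proportions among the rest, with mean e.

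- Kept: [p + (1 - p)e_c] - [p + (1 - p)e_t] = (1 - p)(e_c - e_t).
- Dropped: e_c - e_t, with 2450(1 - p) patients.
- Write P = p + (1 - p)e, so that 1 - P = (1 - p)(1 - e). The two-proportion test statistic when kept, divided by that when dropped, is then sqrt(e/P).

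| Assumed p | Difference multiplied by (kept) | Patients left (dropped) | Ratio of test statistics, e = 0.4 | Ratio for e = 0.2 to 0.6 |
|---|---|---|---|---|
| 0.1 | 0.9 | 2205 | sqrt(0.4/0.46) = 0.93 | 0.845 to 0.968 |
| 0.3 | 0.7 | 1715 | sqrt(0.4/0.58) = 0.83 | 0.674 to 0.913 |
| 0.5 | 0.5 | 1225 | sqrt(0.4/0.70) = 0.76 | 0.577 to 0.866 |

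Both p and e are assumptions. The arithmetic shows that keeping these patients would be the worse choice. It does not show that the plan makes that choice.

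**Which handling does the wording suggest?** A patient who starts at 1.0 and does not change has not progressed to 1.0, so the ordinary reading puts only patients below 1.0 at risk. Protocol 10.2 takes as baseline the last value before the first infusion. An at-risk set defined on that value therefore rests on a pre-treatment measurement, and patients can still be compared by assigned arm. The intent-to-treat default in Protocol 10.2 and SAP 6.1 governs grouping by assignment and does not define who is at risk.

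**Does any output depend on it?** SAP 6.1 says the study stopped about 6 months after the first patient entered. That is well before Week 52, the first scheduled postbaseline CDR-SB, so the only postbaseline value expected is the one at early discontinuation. SAP Table LZBE.6.2 lists no efficacy measure, and CDR-SB is summarized only as a baseline characteristic (SAP 6.5).

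**The case for a change.** The strongest case for a change is that the gap is real. The absolute threshold appears in both documents, and a program written literally to a score of 1.0 or more would count unchanged patients as events. The deferral in Protocol 10.4.2.1 concerns the categorical analyses, so it does not plainly cover this endpoint. One row and a short paragraph would close the gap at no cost in data or visits.

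The description of the text stands. What does not follow is a consequence. The SAP was approved on 08 March 2017, after the study was discontinued, for a synopsis without efficacy analyses. The lack of a time-to-event method there reflects the termination and is not a sign that one was overlooked. Had the trial continued, Protocol 10.2 leaves complete statistical methods to the SAP, where an at-risk rule would have belonged.

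Preferring a change-based event is also a matter of taste here. CDR-SB change from baseline is already a secondary endpoint with its own repeated-measures and slopes analyses, and an absolute milestone adds a different view.

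One uncertainty remains. The documents do not show whether 1.0 was meant as a CDR-SB total, a change in CDR-SB or a CDR global score; SAP 6.5 lists the global score separately. The literal wording favours the total. If another quantity was meant, an at-risk set below a CDR-SB of 1.0 would repair the wrong endpoint.

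**Conclusion.** No change to the plan. The observation is accurate: the threshold is absolute, entry does not cap CDR-SB, and no at-risk set is written. It is, however, a gap in one exploratory row that an analyst would fill sensibly from the row's own words, and under that reading the between-arm difference is not diluted.

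The possible harm, a difference reduced to (1 - p) of its value, depends on the less natural reading and on a share p that the documents do not give. The effect on this trial is nil, because SAP 6.1 plans no efficacy analysis with 26 patients randomized.

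Anyone reusing the definition elsewhere would need to settle what 1.0 refers to, who is at risk, and that event times are known only to the visit (Week 52, Week 104 or early discontinuation). Neither document plans such reuse.

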5.1. Overview of Study Design

Study H8A-MC-LZBE (LZBE) is a multicenter, randomized, double-blind, parallel, placebo-controlled Phase 3 trial comparing solanezumab with placebo for 24 months in approximately 2450 patients with prodromal AD. Patients who meet entry criteria will be randomized in a 1:1 ratio to receive an infusion of solanezumab 400 mg or placebo once every 4 weeks. Patients will be randomized by site and by use of florbetapir PET scanning or CSF for study eligibility (Section 6.1). The primary hypothesis being tested in Study LZBE is that solanezumab will slow the clinical progression of AD as compared with placebo in patients with prodromal AD.

In addition, participants in the ^{18}F -AV-1451 tau imaging addendum will be included in an interim analysis (Section 10.8) designed to assess the relationship between ^{18}F -AV-1451 tau PET and solanezumab treatment.

Three months after the end of the double-blind treatment period (or 4 months after the last dose in case of early discontinuation), patients will come to a follow-up visit for biomarker and safety assessments.

5.2. End of Double-Blind Treatment Period and End of Trial

The analysis of the primary and secondary objectives will use data collected through the end of the double-blind treatment period, defined as Visit 28 (Week 104) for the last patient. The resulting dataset will be used to produce the initial clinical study report (CSR) for the study.

“End of the trial” refers to the date of the last visit or last scheduled procedure shown in the Schedule of Activities (Section 2) for the last patient (including the follow-up visit). The end of the trial will therefore occur after the end of the double-blind treatment period, after the last patient has completed the follow-up visit.

5.3. Scientific Rationale for Study Design

The amyloid hypothesis, as yet unproven, postulates that amyloid-laden neuritic plaques are the first and likely inciting pathological cause of AD-related neurodegeneration (Hardy 1996; Selkoe 1997; Price et al. 1998; Naslund et al. 2000). Therefore, as in most progressive diseases, the earlier the inciting pathology can be removed, the more likely long-term pathological impact will be curtailed. Moving anti-amyloid treatments earlier in the stage of AD is hypothesized to impact cortical neurodegeneration earlier in the disease process and thereby reduce long-term clinical deficits. By addressing AD pathology in the prodromal AD stage, it is theoretically possible to prevent or delay the onset of AD dementia, the stage of AD where patients can no longer perform iADLs independently. The prodromal stage of AD represents a critical stage during which treatment has the potential to slow the progression of disease before sufficient damage is done to the brain to cause dementia.

It should be noted that the stage of AD under study may be referred to as prodromal AD or as MCI due to AD. Prodromal AD, as defined by the IWG (Dubois et al. 2007, 2010, 2014), refers

to the early symptomatic, pre-dementia stage of AD in which clinical symptoms including episodic memory loss of the hippocampal type (characterized by a free recall deficit on testing not normalized with cueing) are present, but not sufficiently severe to affect iADLs and do not warrant a diagnosis of dementia; and in which biomarker evidence from CSF or amyloid PET imaging is supportive of the presence of AD pathological changes. These diagnostic criteria are consistent with those established by the NIA-AA (Albert et al. 2011) for MCI due to AD, which likewise require the presence of a clinical and cognitive syndrome involving cognitive impairment consistent with that associated with AD, preservation of independence in functional abilities, and lack of dementia; and provide guidance on the certainty of degree of diagnosis of MCI due to AD based on biomarker evidence of AD pathology.

5.4. Justification for Dose

A dose of solanezumab 400 mg administered intravenously every 4 weeks was selected based on current preclinical and pharmacodynamic data. This dose is expected to produce reductions in plasma unbound concentrations of A β , which may result in a net increase in the rate of transfer of A β from the CNS compartment to the plasma compartment, as well as show a slowing of cognitive and functional decline in patients diagnosed with prodromal AD.

5.5. Benefit/Risk Assessment

More information about the known and expected benefits, risks, serious adverse events (SAEs) and reasonably anticipated adverse events (AEs) of solanezumab are to be found in the IB.

6. Study Population

Prospective approval of protocol deviations to recruitment and enrollment criteria, also known as protocol waivers or exemptions, are not permitted.

6.1. Inclusion Criteria

Patients are eligible to be included in the study only if they meet all of the following criteria at screening:

Patient Characteristics and Diagnostic Criteria

- [1] Is aged 55-85 years
- [2] Has a diagnosis by the study investigator of a clinical syndrome of cognitive impairment consistent with prodromal AD per IWG diagnostic criteria or MCI due to AD per NIA-AA diagnostic criteria, confirmed by all of the following:
 - a. Subjective cognitive complaint or informant report of cognitive impairment for at least 6 months prior to Visit 1
 - b. No significant impairment of iADLs by patient and informant report and in the judgment of the investigator (that is, patients are maintaining their independence of functioning in daily life with minimal aids or assistance)
 - c. Not demented, based on IWG or NIA-AA guideline criteria
- [3] Scores 17-28 on Montreal Cognitive Assessment (MoCA) at Visit 1
- [4] Scores <27 on free recall cutoff score from the Free and Cued Selective Reminding Test (FCSRT) (Picture version) at Visit 1
- [5] Scores ≤ 4 on Modified Hachinski Ischemia Scale
- [6] Scores >0 on the Functional Activities Questionnaire (FAQ)
- [7] Has a reliable study partner who is in frequent contact with the patient (defined as at least 10 hours per week), will accompany the patient to the study visits, and will be available by telephone at designated times

Note: Study partners must be able to communicate with site personnel and be willing to comply with protocol requirements, and in the investigator's opinion must have adequate literacy to complete the protocol-specified questionnaires. Study partners must come in person to all visits with assessments that require their input.

- [8] Has a florbetapir PET scan or CSF result at screening consistent with the presence of amyloid pathology (see also Exclusion Criterion [34]). (Note: Previously acquired amyloid PET scans unrelated to Study LZBE may be permitted for use in meeting this criterion. Refer to specific guidance in the manual of operations.)

6.2. Exclusion Criteria

Patients will be excluded from study enrollment if they meet any of the following criteria at screening:

Diagnostic Assessments

- [9] Has had MRI or computed tomography (CT) of brain within previous 2 years showing pathology that would be inconsistent with a diagnosis of AD

Medical Conditions

- [10] If female and of childbearing potential, tests positive for pregnancy at Visit 1 on a serum pregnancy test; or does not agree to use 1 highly effective method of contraception or a combination of 2 effective methods of contraception for the entirety of the study
- [11] Lacks adequate venous access for intravenous infusions and blood samples at monthly visits
- [12] Has history of serious infectious disease affecting CNS within previous 5 years
- [13] Has history within previous 5 years of head trauma resulting in protracted loss of consciousness
- [14] Has a current diagnosis of major depressive disorder as per the current Diagnostic and Statistical Manual of Mental Disorders (DSM) or any current primary psychiatric diagnosis other than AD (as per DSM) if, in the judgment of the investigator, the psychiatric disorder or symptom is likely to confound interpretation of drug effect, affect cognitive assessment, or affect the patient's ability to complete the study. Patients with history of schizophrenia or other chronic psychosis are excluded.
- [15] Has history of primary or recurrent malignant disease within previous 5 years, with the exception of successfully treated cutaneous squamous cell carcinoma of the skin, basal cell carcinoma, cervical carcinoma in situ, or in situ prostate cancer with normal prostate-specific antigen post-treatment
- [16] Has any current unstable and/or clinically significant medical condition at Visit 1 that in the investigator's opinion could interfere with participation in the study
- [17] Has known allergy to humanized monoclonal antibodies
- [18] Has history of human immunodeficiency virus (HIV), clinically significant multiple or severe drug allergies, or severe posttreatment hypersensitivity reactions (including, but not limited to, erythema multiforme major, linear immunoglobulin A dermatosis, toxic epidermal necrolysis, or exfoliative dermatitis)
- [19] Has history of chronic alcohol or drug abuse or dependence within the previous 5 years

- [20] Is clinically judged by the investigator to be at serious risk for suicide
- [21] Has electrocardiogram (ECG) abnormalities obtained at Visit 1 that, in the opinion of the investigator, are clinically significant with regard to the patient's participation in the study
- [22] Has alanine aminotransaminase (ALT/SGPT) values ≥ 2 times the upper limit of normal (ULN) of the performing laboratory, aspartate aminotransaminase (AST/SGOT) values ≥ 3 times the ULN, or total bilirubin values ≥ 2 times the ULN, at Visit 1
- [23] Has an ongoing clinically significant laboratory abnormality, as determined by the investigator
- [24] Has Visit 1 MRI with results showing >4 ARIA-H microhemorrhages or presence of ARIA-E (Section 9.3.6)
- [25] Has any contraindications for MRI studies, including claustrophobia, the presence of metal (ferromagnetic) implants, or a cardiac pacemaker that is not compatible with MRI

Prior/Concomitant Therapy

- [26] Has received treatment with a stable dose of an acetylcholinesterase inhibitor (AChEI) or memantine for less than 2 months before randomization. (If a patient has recently stopped an AChEI and/or memantine, he or she must have discontinued treatment at least 2 months before randomization.)
- [27] Has received medications that affect the CNS for less than 4 weeks; note that doses of chronic medications that affect the CNS must be stable for at least 4 weeks before randomization.

Prior/Concurrent Clinical Trial Experience

- [28] Has previously completed or withdrawn from this study or other solanezumab studies, or previous participation in any other study investigating active immunization against A β . Has previously completed or withdrawn from a study of passive immunization against A β with another antibody within the last 120 days.
- [29] Is currently enrolled in a clinical trial involving an investigational product or nonapproved use of a drug or device (other than the investigational product used in this study), or concurrently enrolled in any other type of medical research judged not to be scientifically or medically compatible with this study. Participation in observational studies may be permitted upon review of the observational study protocol and approval by the sponsor.
- [30] Has participated within the last 30 days (for Japan, 4 months) in a clinical trial involving an investigational product. If the previous investigational product has a long half-life, 3 months or 5 half-lives (whichever is longer) should have passed.

Other Exclusions

- [31] Lacks, in the investigator's opinion, adequate premorbid literacy, adequate vision, or adequate hearing to complete the required psychometric tests
- [32] Are investigator site personnel directly affiliated with this study and/or their immediate families, or have study partners who are investigator site personnel directly affiliated with this study. Immediate family is defined as a spouse, parent, child, or sibling, whether biological or legally adopted
- [33] Are Lilly employees or employees of third-party organizations (TPOs) involved in study who require exclusion of their employees, or have study partners who are Lilly employees or are employees of TPOs involved in study who require exclusion of their employees

Exclusion Criteria for Patients Using Lumbar Puncture to Meet Inclusion Criterion [8]

- [34] If using lumbar puncture (LP) to meet Inclusion Criterion [8], a patient will be excluded from having an LP if he or she meets any of the following criteria: has allergy to all local anesthetics (such as lidocaine); has any medical condition requiring treatment with an anticoagulant such as heparin, vitamin K regeneration blockers, or new oral anticoagulants; or has any other contraindication in the opinion of the investigator (for example, suspected increased intracranial pressure or MRI abnormality that would contraindicate LP).

